6.1 Study Procedures

Phase I:

Interested participants will be screened by a trained research assistant using a script. If not eligible or interested, people will be thanked for their time.

If eligible and interested, we will obtain informed consent as previously described. We will also collect data via focus groups, scheduling individual interviews if logistical challenges arise. There will be different semi-structured interview/focus group guides for clinic personnel and patients. Focus groups will be composed of the same subject group – all providers or all patients. Interviews/focus groups with stakeholders will be conducted by the PIs or their designee and a bilingual RA. Participants of focus groups/interviews will be asked to talk about their experiences with patient portals. Specifically, participants will be asked to describe barriers and facilitators to patient portal use for engagement in diabetes care, technology needs, and feedback on the proposed content and procedures of *MAP*.

Providers and CHWs will complete a demographic survey on age, sex, race/ethnicity, type of provider, years in practice, and years at CHC. Adults with T2D will be asked to provide data on age, sex, race/ethnicity, type of insurance, duration of T2D, most recent A1C, and years receiving care at CHC. If adults with T2D cannot recall their most recent A1C, we will ask them to contact their health care provider and provide this information to us at a later date. All interviews/focus groups will be scheduled at convenient times for participants, via ZOOM or in-person if it is safe to do so. If focus groups are conducted via ZOOM, participants will be asked to change their name to a pseudonym prior to entry into the focus group. Interview/focus groups will be conducted in Spanish as needed. Interviews/focus groups will be audiotaped, transcribed verbatim, and Spanish transcripts translated to English. No videos will be recorded for ZOOM interviews.

Phase 2:

For recruitment, flyers will be posted at the clinic and clinicians will be encouraged to refer eligible participants. Information about the study will also be posted on clinic social media channels. Interested recruits will be screened by a language concordant trained RA using a script. If not eligible or interested, people will be thanked for their time.

If eligible and interested, a trained RA will enroll participants from the CHCs. The RA will obtain written informed consent and collect data (in English or Spanish depending on preference). We will use REDCap™, an NIH-supported, FDA-compliant electronic data capture application for data collection and storage. RAs will enter data at the time of data collection into the database via tablets. Trained RAs or nurses will obtain point-of-care A1C values with a fingerstick of blood, following all protocols for safety.

All participants who enroll in the study will receive standard T2D care at their CHC and the *MAP* intervention. The *MAP* intervention consists of 4 components:

1. Supplies/Needs: Provision of tablet, provision of an approximately 6-month data plan (until study completion), and referral for community resources such as food or housing assistance. Participants will keep the tablet after they finish the study. Tablets will be set to the appropriate language (English or Spanish per participants preference).

2. Technology Training: In-person training and ongoing support on how to use the patient portal with their tablet by trained community health workers (CHW) or nurse from the respective clinics. The CHW or nurse will give participants their tablet with data plan. They will meet 1:1 with participants in person or by telehealth. Sessions will cover: 1) how to use the tablet; 2) how to use the portal; 3) social determinants needs assessment; and 4) connection to community resources. The number, duration, and spacing of sessions will be determined by clinical need and participant availability, but it is anticipated that participants will have 4-6 individual sessions of approximately 30 minutes each over the course of the first month of the intervention. Sessions will be conducted face-to-face in the clinic or over secure telemedicine through MyChart/Healow. During the first or second session, the interventionist will conduct a screening for the social determinants of health (eg, housing, food, utilities). According to existing clinic protocol, participants with any such needs will be given referrals to community resources and assistance with accessing them such as completing an application for subsidized housing or obtaining groceries from a food bank.
Attendance will be recorded and CHWs will complete a fidelity checklist after each session. The CHWs will remind participants about sessions. Once technology competence has been established through a teach-back method, participants will be connected with the nurse at each site. Interventionists will remain available after these sessions are concluded, in case participants have additional needs/questions regarding material needs and/or tablet/portal use. Participants will be given the contact information for the interventionist and encouraged to contact them with any questions.
See Appendix X for details of this component of the intervention.
3. Diabetes Support: Diabetes self-management support will be provided by a nurse via the patient portal. The nurse will have an initial in person or telehealth session with participants to assess their diabetes self-management challenges and successes. Nurses will assess for depressive symptoms at their initial session with participants using the PHQ-2 (an established depressive symptom screener for primary care). Participants will be informed of a positive screen and advised to contact their primary care provider or behavioral health professional. Primary care providers will also be informed of a positive screen. At this meeting the nurse and participant will co-create a diabetes self-management plan aligned with their treatment plan prescribed by the participants' primary care provider. The nurse will work with each patient to individualize diabetes behavioral targets, considering the following priorities: use of the portal, attendance at appointments, uploading of blood glucose data to the portal, medication refills and adherence, and lifestyle and emotional factors. After this initial session, the nurse will proactively contact participants via the portal approximately 2 times/week or as clinically indicated for 3 months to check-in, provide diabetes education, provide motivational support, and/or answer any participant questions about their diabetes. After 3 months, the nurse will check-in with participants one time per week. See Appendix X for details of the intervention.
4. Text Messages: CHWs and nurses may also send text message reminders to participants for appointments or to check/use patient portal.

MAP will follow guidelines for health care for low-literacy and low-numeracy patients with diabetes (For example, keeping sessions brief, presenting information in small chunks, use of pictures when possible). In addition, all contacts between the nurse or CHW and participant will be guided by principles of autonomy support. Autonomy support refers to a patient's perception that their healthcare provider recognizes the person's personal agency,

encourages self-efficacy, and supports their self-care choices. Autonomy support is in contrast to simply providing information and is also in contrast to provider attempts to control or coerce patient behavior which can actually hinder engagement in health behaviors.

Interventionist Training

CHWs and nurses from each CHC will receive training on the *MAP* protocol that will entail self-study, small group class sessions, and live practice. Training is anticipated to require the equivalent of approximately 2 days for CHWs and nurses, with homework and practice between training sessions. Training will cover: orientation to research and goals of the study; human subjects protection; protocol and documentation; and, team roles, responsibilities, and supervision. Training will also cover details of the intervention content through materials made for this study. CHWs and nurses will be taught specific strategies for working with low-literacy/low-numeracy individuals.

Training will also teach CHWs and nurses how to provide autonomy support to participants. Research shows that autonomy support can be learned and practiced.⁴⁸⁻⁵¹ Through scripts, role-play, and illustrative case examples, they will be trained to use specific techniques such as acknowledging the participant perspective, identifying participant goals, emphasizing participant responsibility, and providing encouragement. The co-PIs will observe role plays and complete treatment fidelity checklists; CHWs and nurses will be allowed to deliver the intervention to participants only after the PIs judge that their skill level is sufficient. Drs. [name] and [name] have extensive experience training CHWs and nurses in delivery of behavioral interventions. After the formal training, the PIs, the study nurse and CHW will meet approximately weekly during the first four weeks of intervention delivery and bi-weekly thereafter or as indicated by the PIs. Clinics will be compensated for the salary of the nurse and CHW for training, delivering the intervention, and completing study tasks.

Follow-up data will be collected at 3 and 6 months. At each data collection session, an appointment for the next data collection session will be scheduled. Participants will be sent a text message, email message, phone call, or calendar reminder (based on preference) for data collection appointments (3, 2, and 1 day prior). To maximize retention, we will explain all study procedures in the informed consent process, provide escalating incentives for study assessments, and collect data on alternate contact persons. Our research team has ample experience with longitudinal research demonstrating successful retention with hard to reach populations including Latinx adults with T2D. Study participants will receive compensation for data collection (Baseline \$40.00, 3-month \$40.00, 6-month \$60.00)

6.1.1 Data Collection

Phase 1: Data for interviews/focus groups will be conducted using a semi-structured interview guide. Participants – healthcare providers/community health workers and adults with T2D – will participate in one interview or focus group which will last approximately 1 hour and a half. Interview data will provide information on perceived barriers, facilitators, and needs of stakeholders on patient portal use/non-use. Our stakeholders are providers who will be communicating with patients via the patient portal and adults with T2D who will be using the patient portal to learn more about their diabetes and communicate their needs to their provider. Data will be collected via audio-recordings and recordings will be transcribed verbatim. Data will be coded and summarized per established and rigorous procedures. All data will be stored with a participant ID only. The code linking a participant

to their code number will be maintained in a separate file on a secure server at Yale (eg. Secure Box). No identifying data will be included in transcripts (eg. if a name is used that information will not be transcribed).

Phase 2: Participant data for this phase will consist of self-report data by participants (demographic and medical history data, study questionnaires), laboratory data (fingerstick glycosylated hemoglobin A1C), electronic medical record data (e.g. body mass index, recent laboratory data), and patient portal data (e.g., number of logins, number of messages sent/received, content of messages sent/received) (see Table 1). All questionnaires have demonstrated adequate reliability and validity.

Data will also be obtained on program implementation, fidelity, and barriers/facilitators to implementation from meeting field notes.

All data will be stored with a participant ID only. The code linking a participant to their code number will be maintained in a separate file from the data files on a secure computer from Yale. No identifying data from field notes will be recorded.

Table 1: Data Collection	
Sociodemographics	16 items (sex, age, primary language, etc.); Self-rated health (1 item); Charlson comorbidity index (19 items);
Outcome	Measurement
Primary:	
Patient Portal Use	Patient portal data: Number of logins Features used (prescription requested, checked lab, appointment requested) Number of messages sent/received Content of messages Number of blood glucose uploads Number of nurse education materials sent
Glycosylated Hemoglobin (A1C)	A1C now point of care with fingerstick of blood
Secondary:	
Engagement with care	Clinic appointments Referrals ER visits Hospitalizations Use of community resources
T2D clinical management	EMR data: dates of service, A1C, blood pressure, lipid profile, height, weight, BMI
T2D self-management	Self-rated health (1 item); Medication adherence, blood glucose monitoring, healthy eating, physical activity (24 items)
Psychosocial outcomes	Diabetes self-efficacy (8 items) Autonomy support (health care climate) (7 items) Diabetes distress (20 items)
Technology acceptance/use	Digital health literacy (3 items) Technology acceptance (8 items) Technology use (6 items) Technology confidence (4 items) Tablet use (3 items)

	Barriers/Facilitators (13 items)
Satisfaction	Satisfaction with program (4 items) Satisfaction with health care provider (3 items)
Use of community resources	1 items

6.2 Method of Assignment/Randomization (if applicable)

Phase 1: Not applicable

Phase 2: Not applicable

6.3 Adverse Events Definition and Reporting

Phase I: Not applicable

Adverse event means any untoward medical occurrence associated with the use of an intervention in humans, whether or not considered intervention-related.

An adverse event (AE) or suspected adverse reaction is considered "serious" if, in the view of either the investigator or sponsor, it results in any of the following outcomes: death, a life-threatening adverse event, inpatient hospitalization or prolongation of existing hospitalization, a persistent or significant incapacity or substantial disruption of the ability to conduct normal life functions, or a congenital anomaly/birth defect.

For Phase 1, we will be interviewing participants and there is no intervention.

For Phase 2, risk of the study is considered minimal and adverse events are defined in Table 2:

Adverse event	Any untoward or unfavorable medical occurrence in a human subject, including any abnormal abnormal sign (for example, abnormal physical exam or laboratory finding), symptom, or disease, temporally associated with the subject's participation in the research, whether or not considered related to the subject's participation in the research
Serious adverse event	Any adverse event that: 
 1. results in death; 2. is life-threatening (places the subject at immediate risk of death from the event as it occurred); 3. results in inpatient hospitalization or prolongation of existing hospitalization; (e.g., hospitalization for asthma or hypoglycemia) 4. results in a persistent or significant disability/incapacity; 5. results in a congenital anomaly/birth defect; or 6. based upon appropriate medical judgment, may jeopardize the subject's health and may require medical or surgical intervention to prevent one of the other outcomes listed in this definition (e.g., allergic bronchospasm requiring intensive treatment in the emergency room or at home, convulsions that

	do not result in inpatient hospitalization, or the development of drug dependency or drug abuse).
Unanticipated problems	
Any incident, experience, or outcome that meets all of the following criteria:
 
 1. unexpected (in terms of nature, severity, or frequency) given (a) the research procedures that are described in the IRB-approved research protocol and informed consent document; and (b) the characteristics of the subject population being studied; 2. related or possibly related to participation in the research (reasonable possibility that the incident, experience, or outcome may have been caused by the procedures involved in the research); and 3. suggests that the research places subjects or others at a greater risk of harm (including physical, psychological, economic, or social harm) than was previously known or recognized.

The research team will meet with RNs at least every 2 weeks during study implementation. The RNs, CHW, and/or research team will report adverse events or unanticipated problems that they identify during the intervention implementation at research meetings. The PIs will solicit more information about the event if needed and will determine if it's serious or unanticipated, using the definitions identified in the table above. Serious adverse events, deaths or unanticipated problems involving risk to subjects encountered during the study will be reported by phone as soon as identified to the Institutional Review Board at Yale. In addition, the PI will follow-up immediately to elicit as much information as possible about the event. The PI is responsible for complying with all regulations concerning the reporting of serious adverse events. The decision to terminate participation for a study participant due to an adverse experience rests with the investigator who is responsible until the study is completed or adverse events are stable or resolved. In making termination decisions, the PI may carry out discussions with Co-Investigators, consultants, or other personnel. If the IRB determines that the adverse event was attributable to the intervention, the PI will notify the NIH grant administrator within 72 hours of receipt of the IRB decision.

6.4 Reaction Management

Phase 1: Not applicable

Phase 2: All participants will be receiving care at a community health center. Participants will be referred to appropriated help, resources, or clinical care as needed.

6.5 Withdrawal Procedures

Phase 1: Not applicable

Phase 2: Participants will be informed that their participation in the study is voluntary and they are free to withdraw at any time and withdrawal from the study will not affect their relationships with anyone at the clinic. Participants who withdraw from the study will keep the tablet provided from the study.

Withdrawal of enrolled participants who develop any of the exclusionary or potentially exclusionary criteria (e.g., pregnancy) will be assessed on a case by case basis depending on the severity and whether there are any potential risks to following the study protocol. The decision to withdraw a participant from the study will be ultimately made by the co-PIs. Data and/or sample collection will be discontinued depending on the severity of the condition. Should a participant develop an exclusionary condition, he or she will be given the opportunity to continue. He or she will also be given the opportunity to opt out from data collection even when the co-PIs had considered appropriate to continue collecting data.

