5.3 Eligibility Criteria

Phase 1 eligibility criteria for adults with T2D

In order to be eligible for inclusion in the study, an individual must meet all of the following criteria:

- Established patient of one of the partner CHCs;
- Age ≥ 18 years;
- Diagnosed with T2D ≥ 6 months;
- Able to read in English or Spanish.

Any individual who meets any of the following criteria will be excluded from participation in this study:

Cognitive impairment (≥ 3 errors on the Six Item Screener for cognitive impairment in clinical research [SIS]) (Callahan et al. 2002) as they will have difficulty in completing the study requirements

Gestational diabetes

Diagnosis of type 1 diabetes

Phase 1 eligibility criteria for health care providers

In order to be eligible for inclusion in the study, an individual must meet all of the following criteria:

Health care provider or community health worker at one of our partner CHC

Provides care/services for adults with T2D

Any individual who meets any of the following criteria will be excluded from participation in this study:

None

Vulnerable/special populations that will be included are: economically or educationally disadvantaged populations and elderly populations (who do not demonstrate cognitive impairment). These groups have health disparities with respect to patient portal use and are important to include in the research to be able to address their needs and improve health equity and health outcomes.

Phase 2: Inclusion criteria are: established patient of one of the partner CHCs; age 18 years or older; diagnosed with T2D >6 months; most recent A1C >7.5%; no current use of patient portal, no intention of moving/changing clinic within 6 months; and able to read in English or Spanish. Exclusion criteria include: cognitive impairment and gestational diabetes.

Participants who participated in Phase 1 will be eligible to participate in Phase 2.

Vulnerable/special populations that will be included are: economically or educationally disadvantaged populations and elderly populations (who do not demonstrate cognitive impairment). These groups have health disparities with respect to patient portal use and are important to include in the research to be able to address their needs and improve health equity and health outcomes.

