6.6 Locations/Facilities

Phase 1: Interviews/focus groups, if able to be scheduled in-person, will be conducted at the CHC in a private room. Our clinic locations are Fair Haven Community Health Center in New Haven and Norwalk Community Health Center in Norwalk, CT. Interviews/focus groups may also be conducted by phone or ZOOM. We will provide participants access to ZOOM and instructions how to use it, if they are not familiar with this platform.

Phase 2: Data collection will be collected from participants in-person at the clinic or private location preferred by participants or via telehealth for study questionnaires. A1C data will be collected at the clinic or private location preferred by participants. Electronic health record and patient portal data will be collected by trained clinic personnel at each clinical site.

7 Statistical Design

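### Sections 6.5 and 6.3 do not separate stopping MAP from stopping outcome collection, so portal logins and EMR outcomes may be lost for health-related reasons although clinic staff could still export them

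*Combined protocol and SAP*

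**What the plan says.** Section 6.5 sets the trigger: "Withdrawal of enrolled participants who develop any of the exclusionary or potentially exclusionary criteria (e.g., pregnancy) will be assessed on a case by case basis". For Phase 2, Section 5.3 states: "Exclusion criteria include: cognitive impairment and gestational diabetes". Pregnancy, the example in 6.5, is not itself on that list, and the protocol does not define a potentially exclusionary criterion.

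On who decides, 6.5 says "The decision to withdraw a participant from the study will be ultimately made by the co-PIs", and two sentences later "Should a participant develop an exclusionary condition, he or she will be given the opportunity to continue". On data, it says "Data and/or sample collection will be discontinued depending on the severity of the condition". Its last sentence lets a participant opt out of data collection even where the co-PIs would have kept collecting. It also says: "Participants who withdraw from the study will keep the tablet provided from the study".

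Section 6.3 adds a second route: "The decision to terminate participation for a study participant due to an adverse experience rests with the investigator". It is silent on data collection after that point.

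On data sources, Section 6.6 says "Electronic health record and patient portal data will be collected by trained clinic personnel at each clinical site", and Section 8.5 describes how clinic staff extract, de-identify and transfer these data. Logins over the past 3 months are a primary outcome (4.2.1). The other primary outcome, A1C, is a study fingerstick; EMR A1C is a separate secondary outcome (Table 1). ER visits and hospitalizations are secondary outcomes (4.2.2), and Table 1 names no source for them.

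**The concern.** A rule that ends data collection according to severity makes health status a reason for missing outcomes. Stopping an intervention and stopping the measurement of its effect are different decisions, and the protocol does not treat them separately. For logins the loss is avoidable, because no visit is needed and a participant who withdraws keeps the tablet and may go on using the portal.

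The planned analyses do not address this kind of loss. Section 7.2 fits a random-intercept mixed model by maximum likelihood to participants with a baseline and at least one later value. Sections 7.2 and 7.7 repeat it with multiple imputation from a multivariate normal model of the repeated A1C values. Both rest on missing at random. Neither, as described, uses severity or the reason for stopping, and no analysis departs from that assumption.

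Phase 2 aims to estimate effect sizes (3.3) for a future larger study (7.1), so an estimate that leans on those who stayed would be carried forward.

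**Working it through.** **1. Which outcomes depend on a visit**

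| Outcome | Source in the protocol | Study visit or contact needed? |
|---|---|---|
| Logins (primary) | Portal data, clinic personnel (6.6, 8.5) | No |
| A1C (primary) | Study fingerstick (Table 1, 6.6) | Yes |
| EMR A1C, blood pressure, lipids, BMI (secondary) | EMR, clinic personnel (6.6, 8.5) | No |
| ER visits, hospitalizations (secondary) | Not named in Table 1 | Unknown |
| Questionnaires (secondary) | Participant report (6.1.1) | Yes |

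A severity rule can be needed only for the rows that involve the participant.

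**2. The stated precision, as a yardstick**

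Section 7.1 gives an SD of change of 0.72, n = 30, a standard error of 0.13 and a margin of ±0.27.

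- SE = 0.72/√30 = 0.131.
- Half-width = t(0.975, 29) × SE = 2.045 × 0.131 = 0.269. This agrees with the plan.

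The 0.72 itself does not follow from the SD of 1.2 and correlation of 0.57 in the same paragraph: 1.2 × √(2 × (1 − 0.57)) = 1.113, which gives a half-width of 0.416. That is a separate matter. The stated 0.27 serves below only as a yardstick.

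**3. Loss of precision**

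If 1, 3 or 6 of 30 lose all later A1C values, the half-width rises from 0.269 to 0.274, 0.285 or 0.304 (SD 0.72), or from 0.416 to 0.423, 0.440 or 0.470 (SD 1.113). This is minor.

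**4. Possible bias in A1C change**

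If m of 30 are missing and their mean change differs by d from that of the others, the mean in those observed differs from the mean in all 30 by (m/30) × d. The protocol gives neither m nor d; both are assumed.

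| m | d = 0.5 | d = 1.0 | d = 1.5 |
|---|---|---|---|
| 1 | 0.02 | 0.03 | 0.05 |
| 2 | 0.03 | 0.07 | 0.10 |
| 3 | 0.05 | 0.10 | 0.15 |
| 6 | 0.10 | 0.20 | 0.30 |

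This describes participants with no later value, whom the mixed model leaves out. Someone with a 3-month value stays in the model, and that value recovers part of the loss.

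**5. Possible bias in logins**

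Assume, for illustration, 20 logins in 3 months among those observed and 3 among those lost.

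- m = 1: true mean = 20 − 17/30 = 19.43; 20/19.43 = 1.03, an overestimate of 3%.
- m = 2: 20 − 34/30 = 18.87; 20/18.87 = 1.06, or 6%.
- m = 3: 20 − 51/30 = 18.3; 20/18.3 = 1.09, or 9%.

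Eligibility requires no current portal use (5.3), so baseline counts should be near zero for everyone. They say little about later logins, and the model has little from which to predict a lost value.

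**6. Hospitalizations**

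Inpatient hospitalization is a serious adverse event (6.3, Table 2) and also a secondary outcome, counted over the previous 3 months (Synopsis, Outcome Variables). If, for illustration, 3 of 30 are hospitalized and one is terminated before the count, the observed proportion is 2/29 = 6.9% instead of 3/30 = 10%. The event would still be in the safety record; the protocol does not say that it enters the outcome.

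**The case against.** The strongest reply is that the rule is narrow. It applies to exclusionary or potentially exclusionary criteria, and only two are listed for Phase 2. A reader might infer that any new illness ends data collection; 6.5 does not say so. Nor does it say that data always stop, since its last sentence foresees cases where collection continues, and 6.3 concerns participation and is silent on data. So outcomes may go missing; the text does not show that they will.

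A reader might also infer that most outcomes, including the primary A1C, could be collected passively. The documents do not support that: the primary A1C is a fingerstick, EMR A1C is a different measure, and the source for hospital use is not given. Dependence on health does not by itself violate missing at random either. It does so only if missingness still depends on unobserved outcomes once the observed data are taken into account.

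Losses of 10% to 30% among people who log in rarely would describe disengagement, not this rule. A participant who stops using the portal without withdrawing still has logins exported. A hospitalization that leads to termination is also already reported as a serious adverse event.

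The severity rule may have a purpose for active procedures: 6.5 ties the assessment to possible risks of following the protocol, and someone who develops cognitive impairment may raise questions of capacity. All of this limits the point. What stands is that 6.5 states a rule for ending data collection without exempting record data, and nothing elsewhere in the protocol keeps record-based follow-up going.

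**Conclusion.** The point holds as a low-cost improvement. Following 6.5 as written can lose a primary outcome, logins, together with EMR outcomes, for health-related reasons and without need. This can break the assumption shared by the main analysis and its multiple-imputation rerun, so agreement between the two would give no reassurance on it.

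The size is uncertain because the protocol gives no withdrawal rate. With one or two of 30 affected it is small: 0.02 to 0.10 in mean A1C change and 3% to 6% in mean logins, on the assumed differences above. It approaches the stated A1C margin of 0.27 only if about six are lost and their change differs by around 1.5 points. The A1C figures also cover a measure that the fix can protect only in part, since the fingerstick needs the participant.

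The sentences in 6.5 on the co-PIs' final say and on the participant's chance to continue are in tension. They can be read together, as an offer that stands unless the co-PIs withdraw the person, but the text does not say so. A reader might infer that the two sites could decide differently; the text gives the final decision to the co-PIs, so that does not follow.

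**What to change.** In Sections 6.3 and 6.5:

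- State that when MAP or study visits stop for any reason, portal logins and EMR outcomes are still exported at 3 and 6 months, unless the participant withdraws permission for record data.
- Limit the severity-based rule to active procedures (fingerstick and questionnaires), which may still be offered where the investigators judge it appropriate.
- Reconcile the sentences in 6.5 on the co-PIs' decision and the participant's opportunity to continue. Which one stands is for the investigators.

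In Table 1, name the data source for ER visits and hospitalizations, and state that a hospitalization already reported as a serious adverse event counts in that outcome.

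The cost is protocol wording, consent wording that distinguishes stopping the intervention from withdrawing permission for record data, and a few extra rows in exports that the clinics already make. The reported change may come out somewhat smaller, because it would then cover more of those enrolled.
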